6.6.2.3 Management of Diarrhea

An anti-diarrheal agent should be recommended to the participant at the start of study treatment and participants should be instructed and educated to initiate anti-diarrheal treatment at the first onset of soft bowel movements. The choice of anti-diarrheal agent should be individualized to the participant's clinical circumstances and follow standard medical practice. If signs/symptoms of diarrhea persist despite optimal medical management, instructions contained in [Table 5](#) should be followed.

6.6.2.4 Management of Hepatotoxicity

Liver function tests (alanine transaminase [ALT], aspartate transaminase [AST], bilirubin levels) should be conducted as detailed in the SoA (Section 1.3) and as clinically indicated. If signs/symptoms indicating liver injury occur, instructions contained in [Table 5](#) should be followed. Appropriate supportive care should be provided together with close monitoring. If hepatic failure occurs, lenvatinib must be discontinued.

6.6.2.5 Management of Thromboembolic Events

Participants should be advised to pay attention to symptoms suggestive of venous thromboembolic events which include acute onset of shortness of breath, dyspnea, chest pain, cough, hemoptysis, tachypnea, tachycardia, cyanosis, DVT signs including lower-extremity swelling, and warmth to touch or tenderness. In case any of these symptoms appear, participants should be instructed to report such symptoms promptly to the treating physician. If a thromboembolic event is confirmed, instructions contained in [Table 5](#) should be followed. Appropriate supportive care should be provided together with close monitoring. If a participant experiences a Grade 3 or a life-threatening (Grade 4) thromboembolic reaction, including pulmonary embolism, lenvatinib must be discontinued.

Arterial thromboembolic events (eg, new onset, worsening, or unstable angina, myocardial infarction, transient ischemic attack, and cerebrovascular accident) of any grade require study treatment discontinuation.

6.6.2.6 Management of Posterior Reversible Encephalopathy Syndrome/Reversible Encephalopathy Syndrome/ Reversible Posterior Leukoencephalopathy Syndrome

Posterior Reversible Encephalopathy Syndrome/Reversible Encephalopathy Syndrome/ Reversible Posterior Leukoencephalopathy Syndrome (PRES/RPLS) is a neurological disorder that can present with headache, seizure, lethargy, confusion, altered mental function, blindness, and other visual or neurological disturbances. Mild to severe hypertension may be present. MRI is necessary to confirm the diagnosis of PRES/RPLS. Appropriate measures should be taken to control BP. In participants with signs or symptoms of PRES/RPLS, instructions in [Table 5](#) should be followed.

6.6.2.7 Management of Hypocalcemia

Serum calcium should be monitored per the SoA (Section 1.3). Corrected serum calcium should be used to assess the grade of hypocalcemia per CTCAE v4.0, using the following formula:

$$\text{Corrected calcium} = ([4 - \text{serum albumin in g/dL}] \times 0.8 + \text{serum calcium})$$

The formula is not applicable when serum albumin concentration is normal (>4 g/dL); in such situations, the total (uncorrected) serum calcium should be used instead.

Hypocalcemia should be treated per institutional guidelines (eg, using appropriate calcium, magnesium, and Vitamin D supplementation) until resolution.

6.6.2.8 Management of Hemorrhage

Instructions in [Table 5](#) should be followed for the management of hemorrhage. Either resume at a reduced dose or discontinue lenvatinib depending on the severity and persistence of hemorrhage.

6.6.2.9 Management of Gastrointestinal Perforation or Fistula Formation

Lenvatinib should be discontinued in any participants who develop gastrointestinal perforation of any grade or Grade 4 fistula.

See Section 10.7 (Appendix 7) for country-specific requirements.

6.6.2.10 Management of QT Prolongation

Lenvatinib should be withheld in the event of development of QT interval prolongation greater than 500 msec. Lenvatinib should be resumed at a reduced dose when QTc prolongation is resolved to <480 msec or baseline. Monitor potassium, calcium and magnesium, and replenish as appropriate.

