Note: Participants who have entered the follow-up phase of an investigational study may participate as long as it has been 4 weeks after the last dose of the previous investigational agent.

Diagnostic Assessments

19. Has urine protein ≥ 1 g/24h. Participants with proteinuria $>1+$ on urine dipstick testing will undergo 24-hour urine collection for quantitative assessment of proteinuria.

20. Has prolongation of QTc interval (calculated using Fridericia's formula) to >480 ms.

Note: If the QTcF is prolonged to >480 ms in the presence of a pacemaker, contact the Sponsor to determine eligibility.

21. Has left ventricular ejection fraction (LVEF) $<55\%$ as determined by multigated acquisition scan (MUGA) or echocardiogram (ECHO).

22. Has a diagnosis of immunodeficiency or is receiving chronic systemic steroid therapy (in dosing exceeding 10 mg daily of prednisone equivalent) or any other form of immunosuppressive therapy within 7 days prior the first dose of study intervention.

23. Has known active CNS metastases and/or carcinomatous meningitis. Participants with previously treated brain metastases may participate provided they are radiologically stable (ie, without evidence of progression by imaging) for at least 4 weeks by repeat imaging (note that the repeat imaging should be performed during study screening), clinically stable and without requirement of steroid treatment for at least 14 days before first dose of study intervention. GBM participants are exempt.

Note: MRI brain scan will be conducted for all participants with stable brain metastases at screening. Brain CT scan should only be conducted when MRI is contraindicated.

24. Has tumors involving the brain stem.

25. Has severe hypersensitivity (\geq Grade 3) to pembrolizumab and/or any of its excipients.

26. Has an active autoimmune disease that has required systemic treatment in past 2 years (ie, with use of disease modifying agents, corticosteroids or immunosuppressive drugs). Replacement therapy (eg, thyroxine, insulin, or physiologic corticosteroid replacement therapy for adrenal or pituitary insufficiency) is not considered a form of systemic treatment and is allowed.

27. Has a history of (noninfectious) pneumonitis that required steroids or has current pneumonitis.

28. Has an active infection requiring systemic therapy.
29. Has a known history of human immunodeficiency virus (HIV) infection. No HIV testing is required unless mandated by local health authority.

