6.6.2 Lenvatinib

Lenvatinib dose reduction and interruption for participants who experience lenvatinib- or lenvatinib-pembrolizumab combination therapy-related toxicity will be in accordance with the dose modification guidelines described in [Table 5](#). An interruption of study treatment for more than 28 days will require Sponsor approval before treatment can be resumed.

The starting dose of lenvatinib is 20 mg/day for participants enrolled in the combination therapy arm (Arm 1). Lenvatinib dose reductions for Arm 1 occur in succession based on the previous dose level (14, 10, and 8 mg/day). Any dose reduction below 8 mg/day must be discussed with the Sponsor.

The starting dose of lenvatinib is 24 mg/day for participants enrolled in the monotherapy arm (Arm 2). Lenvatinib dose reductions for Arm 2 will take place in succession based on the previous dose level (20, 14, and 10 mg/day). Any dose reduction below 10 mg/day must be discussed with the Sponsor.

For both Arm 1 and Arm 2, once the lenvatinib dose has been reduced, it may not be increased at a later date, unless the dose has been mistakenly decreased; in this situation, the Sponsor's approval is required to increase the dose.

Refer to the subsections below for management of hypertension (Section 6.6.2.1), proteinuria (Section 6.6.2.2), diarrhea (Section 6.6.2.3), hepatotoxicity (Section 6.6.2.4), thromboembolic events (Section 6.6.2.5), posterior reversible encephalopathy syndrome/reversible posterior leukoencephalopathy syndrome (PRES/RPLS; Section 6.6.2.6), hypocalcemia (Section 6.6.2.7), hemorrhage (Section 6.6.2.8), gastrointestinal perforation or fistula formation (Section 6.6.2.9), QT prolongation (Section 6.6.2.10), and osteonecrosis of the jaw (Section 6.6.2.11) as appropriate, before consulting the dose modification table ([Table 5](#)). For overlapping toxicities of pembrolizumab and lenvatinib, please refer to Section 6.6.3.

See Section 10.7 (Appendix 7) for country-specific requirements.

Table 5 Dose Modification Guidelines for Lenvatinib-Related Adverse Events

Treatment-Related Toxicity ^{a,b}	Management	Dose Adjustment
Grade 1 or Tolerable Grade 2		
	Continue treatment	No change
Intolerable Grade 2^{c,d} or Grade 3^{e,f}		
First occurrence	Interrupt lenvatinib until resolved to Grade 0-1, or tolerable Grade 2	Arm 1: Reduce lenvatinib dose from 20 mg QD to 14 mg QD (1-level reduction) Arm 2: Reduce lenvatinib dose from 24 mg QD to 20 mg QD (1-level reduction)

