Second occurrence (same toxicity or new toxicity)	Interrupt lenvatinib until resolved to Grade 0-1, or tolerable Grade 2	Arm 1: Reduce lenvatinib dose from 14 mg QD to 10 mg QD (1-level reduction) Arm 2: Reduce lenvatinib dose from 20 mg QD to 14 mg QD (1-level reduction)
Third occurrence (same toxicity or new toxicity)	Interrupt lenvatinib until resolved to Grade 0-1, or tolerable Grade 2	Arm 1: Reduce lenvatinib dose from 10 mg QD to 8 mg QD (1-level reduction) Arm 2: Reduce lenvatinib dose from 14 mg QD to 10 mg QD (1-level reduction)
Fourth occurrence (same toxicity or new toxicity)	Interrupt lenvatinib	Discuss with Sponsor
Grade 4^g: Discontinue Study Treatment		

Abbreviations: AE=adverse event; BMI=body mass index; CTCAE=Common Terminology Criteria for Adverse Events; QD=once daily.

Note: For grading see CTCAE version 4.0. Collect all AE grades (ie, decreasing and increasing CTCAE grade).

- a. An interruption of study treatment for more than 28 days will require Sponsor's approval before treatment can be resumed.
- b. Initiate optimal medical management for nausea, vomiting, hypertension, hypothyroidism and/or diarrhea prior to any lenvatinib interruption or dose reduction.
- c. Applicable only to Grade 2 toxicities judged by the participant and/or physician to be intolerable.
- d. Obese participants (BMI ≥ 30) with weight loss do not need to return to the baseline weight or within 10% of their baseline weight (ie, Grade 1 weight loss). These participants may restart study intervention at a lower dose once their weight remains stable for at least 1 week and they reach at least a BMI of 25. The new stable weight should be used as the new baseline for further dose reductions.
- e. For asymptomatic laboratory abnormalities, such as Grade ≥ 3 elevations of amylase and lipase that are not considered clinically relevant by the investigator, continuation of treatment should be discussed with Sponsor.
- f. For Grade 3 thromboembolic event, permanently discontinue lenvatinib. See Section 6.6.2.5.
- g. Excluding laboratory abnormalities judged to be non-life-threatening, in which case manage as Grade 3.

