8.3.3 Electrocardiograms

Electrocardiograms (ECGs) will be obtained as designated in the SoA (Section 1.3). Complete, standardized, 12-lead ECG recordings that permit all 12 leads to be displayed on a single page with an accompanying lead II rhythm strip below the customary 3×4 lead format are to be used. In addition to a rhythm strip, a minimum of 3 full complexes should be recorded from each lead simultaneously. Participants must be in the recumbent position for a period of 5 minutes before the ECG. The Fridericia correction method for calculating QTc will be used.

An ECG abnormality may meet the criteria of an AE as described in this protocol (see Appendix 3) and the CRF Completion Guidelines. In these instances, the AE corresponding to the ECG abnormality will be recorded on the appropriate CRF.

QTc prolongation has been seen in some lenvatinib studies. Monitor ECGs every cycle (as specified in the SoA) in participants with congenital long QT syndrome, congestive heart failure, bradyarrhythmias, or those who are taking drugs known to prolong the QTc interval (including class Ia and III antiarrhythmics). Refer to the lenvatinib IB.

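### The lenvatinib hold for QT prolongation is written on uncorrected QT (>500 msec) but the restart on QTc (<480 msec), so the two limits conflict at slow heart rates and leave a gap above 60 bpm

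*Combined protocol and SAP*

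**What the plan says.** Section 6.6.2.10 gives two consecutive instructions. The first is "Lenvatinib should be withheld in the event of development of QT interval prolongation greater than 500 msec". The second allows restart at a reduced dose "when QTc prolongation is resolved to <480 msec or baseline".

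Where the protocol says how the interval is calculated, it uses the Fridericia correction. Exclusion criterion 20 in Section 5.2 begins "Has prolongation of QTc interval (calculated using" Fridericia's formula and sets the limit at >480 ms. Section 8.3.3 states "The Fridericia correction method for calculating QTc will be used", and it names the signal seen in lenvatinib studies as prolongation of QTc.

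Two rules in Section 6.6.2 bear on the consequences:

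- On reductions: "once the lenvatinib dose has been reduced, it may not be increased at a later date, unless the dose has been mistakenly decreased". Even then, the Sponsor must approve the increase.
- On order of use: the toxicity-specific subsections are to be read "as appropriate, before consulting the dose modification table", that is, ahead of Table 5.

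**The concern.** The two limits form one stop-and-restart rule, so they need to be on the same scale. QT and QTcF coincide only at 60 bpm and move apart as the heart rate moves away from it. A site that applies the first sentence as written compares the uncorrected interval with 500 msec, then compares the corrected interval with 480 msec to decide on restart.

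Two errors follow:

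- **Slow heart rates.** A participant can be held, and restarted only at a lower dose, when QTcF was never above the restart limit. Section 6.6.2 makes that reduction difficult to reverse, since a site that followed the text literally has not obviously made a mistake.
- **Heart rates above 60 bpm.** A participant with QTcF above 500 msec can fail to meet this section's trigger and stay on daily lenvatinib. This is the more serious direction. After Cycle 2 Day 1, the Schedule of Activities calls for routine ECGs only about every 12 weeks unless the participant is high-risk, so a missed trigger may not be looked at again for some time.

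Slow rates are foreseen in the protocol. Section 8.3.3 puts participants with bradyarrhythmias on ECG monitoring every cycle, and the France appendix (Section 10.7.1) warns about resting rates under 50 bpm.

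**Working it through.** There is no power or precision figure to reproduce. The check is to put both limits on one scale.

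**Inputs**

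- Hold: QT > 500 msec (Section 6.6.2.10).
- Restart: QTc < 480 msec or baseline (Section 6.6.2.10).
- Correction: Fridericia (Section 8.3.3), QTcF = QT / (60/HR)^(1/3), with HR in beats per minute.

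**Where the limits cross**

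- QT 500 equals QTcF 480 when (60/HR)^(1/3) = 500/480 = 1.0417, so HR = 60/1.0417³ = 53.1 bpm. Below this, a QT just over 500 meets the hold and the restart limit together.
- QT 500 equals QTcF 500 when (60/HR)^(1/3) = 1, so HR = 60 bpm. Above this, QTcF can pass 500 while QT is still at or below 500.

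**Size of each band**

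| HR (bpm) | QTcF when QT = 500 | QT at which QTcF = 480 | QT at which QTcF = 500 |
|---|---|---|---|
| 45 | 454.3 | 528.3 | 550.3 |
| 50 | 470.5 | 510.1 | 531.3 |
| 60 | 500.0 | 480.0 | 500.0 |
| 70 | 526.4 | 456.0 | 475.0 |
| 80 | 550.3 | 436.1 | 454.3 |
| 100 | 592.8 | 404.8 | 421.7 |

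*Conflict at slow rates* (hold and restart both met): QT from 500 up to 510 msec at 50 bpm, and from 500 up to 528 msec at 45 bpm. Example: QT 505 at 45 bpm gives 505/1.1006 = 458.8 msec, which is over the hold limit but already well under the restart limit.

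*Gap at faster rates* (QTcF above 500, hold not met): QT 475 to 500 msec at 70 bpm, 454 to 500 at 80 bpm, and 422 to 500 at 100 bpm. Example: QT 430 at 100 bpm gives 430/0.8434 = 509.8 msec, with no hold under this section.

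**Sensitivity to the formula.** The crossover would be 55.3 bpm under Bazett, 53.1 under Framingham and 48.6 under Hodges. The 60 bpm bound is the same under all of them.

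**After correction.** With the hold on QTcF > 500 and the restart on QTcF < 480, the limits are 20 msec apart at every heart rate. The conflict and the gap both disappear.

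**The case against.** The best reply is that the meaning can be recovered from the paragraph. The restart sentence speaks of QTc prolongation having resolved, and the only thing it can refer back to is the prolongation that caused the hold. The protocol also uses QT prolongation as a general name for the toxicity: in the heading of 6.6.2.10, in the cross-reference in 6.6.2 and in the France appendix. On that view the first sentence is shorthand. This is a good argument about intent, and I accept that QTc was probably meant. It does not supply a definition. The first sentence attaches a number to the QT interval, and the next sentence uses a different term.

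The second reply is that Table 5 is a backstop. Section 8.3.3 notes "An ECG abnormality may meet the criteria of an AE as described in this protocol", and for treatment-related Grade 3 or intolerable Grade 2 events Table 5 says "Interrupt lenvatinib until resolved to Grade 0-1, or tolerable Grade 2". It discontinues treatment for Grade 4. So the gap lies in Section 6.6.2.10 and not necessarily in the protocol as a whole. That stands, with a limit: this route depends on the finding being recorded as an AE and graded, and the documents do not reproduce the CTCAE grades for QTc. How many of the missed cases Table 5 would catch cannot be settled from them.

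Third, the error at slow rates is on the cautious side and covers narrow QT bands, and a mistaken reduction can be reversed with Sponsor approval. That is fair, and it is why the faster-rate gap carries more weight.

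**Conclusion.** The concern holds. Section 6.6.2.10 is wrong as written: its hold and restart limits are on different scales, and no text reconciles them. Read literally, they conflict below about 53 bpm and leave a gap above 60 bpm, which includes ordinary rates such as 70 to 80 bpm, where QTcF can reach 526 to 550 msec without meeting the section's trigger.

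The 53 bpm figure assumes the Fridericia correction, which the protocol specifies. The consequences assume that a site applies the first sentence literally. The documents give no distribution of heart rate or on-treatment QTc, so the number of participants affected cannot be estimated. It is probably small, since QTcF above 480 ms is excluded at entry. The issue concerns dosing safety and leaves the efficacy analysis untouched. It should be corrected, but it does not threaten the trial's conclusions.

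**What to change.** State both limits in Section 6.6.2.10 as QTcF: withhold lenvatinib for QTcF >500 msec, and restart at a reduced dose once QTcF is <480 msec or back to baseline. The threshold values stay as they are.

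The cost is one term in each of two sentences and a clarification to sites. No new measurement is needed, because Section 8.3.3 already requires the Fridericia correction whenever QTc is calculated.

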6.6.2.11 Management of Osteonecrosis of the Jaw

Perform an oral examination prior to treatment with lenvatinib and periodically during lenvatinib treatment. Advise participants regarding good oral hygiene practices. Avoid invasive dental procedures, if possible, while on lenvatinib treatment, particularly in participants at higher risk. For participants requiring invasive dental procedures, discontinuation of bisphosphonate treatment may reduce the risk of ONJ. Withhold lenvatinib if ONJ develops and restart based on clinical judgement of adequate resolution (See Section 6.6.4).

6.6.3 Dose Modifications for Overlapping Toxicities

Based on the known toxicity profiles of pembrolizumab and lenvatinib, certain treatment-related AEs are uniquely associated with one drug versus the other. For example, hypertension, arterial thrombotic events, proteinuria, and hemorrhagic events are known risks for lenvatinib treatment, while immune-related AEs are risks for pembrolizumab treatment. However, certain AEs, such as such as diarrhea, hypothyroidism, and liver enzyme elevation, may be initially considered attributable to either study drug. Therefore, evaluation of attribution is important for determining the study drug most likely related to the AE, or an alternative etiology, and subsequently proper clinical management. The following aspects should be considered:

1. Timing of AE onset

Since lenvatinib is dosed daily and continuously due to a relatively short half-life (28 hours), and pembrolizumab is dosed Q3W due to a long half-life, lenvatinib can be interrupted to assess whether an AE improves/resolves with dechallenge (ie, interruption of treatment) based on the following 2 scenarios:

- If an AE is identified during a treatment cycle (ie, between 2 pembrolizumab doses), only lenvatinib dose interruption is needed.
- If an AE is identified at the beginning of a treatment cycle, lenvatinib can be interrupted and dosing of pembrolizumab should be held.

If the participant recovers from an AE in response to lenvatinib interruption (ie, positive dechallenge), the event is more likely to be related to lenvatinib. Otherwise, after excluding other alternative explanations, an immune-related AE should be considered.

2. Severity of AE

If an AE is suspected to be treatment-related and is severe/life-threatening at the time of onset or is rapidly worsened, action including interrupting both drugs and initiating treatment with a corticosteroid (with exception of hypothyroidism, T1DM) and other supportive care should be taken promptly.

3. Participants receiving the combination therapy (pembrolizumab + lenvatinib) must discontinue study therapy if any of the following occur:

- ALT or AST >5 X ULN for more than 2 weeks.

Pembrolizumab will have already been permanently discontinued per [Table 3](#), but lenvatinib may be administered at a reduced dose by the time this criterion is met and must be permanently discontinued immediately.

- ALT or AST $>3 \times$ ULN and (TBL $>2 \times$ ULN or INR >1.5)
Although [Table 3](#) advises pembrolizumab to be withheld (interrupted), and [Table 5](#) advises lenvatinib to have no dose modification or a reduction, if this criterion is met, both drugs must be permanently discontinued immediately.

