The investigator is responsible for review of medical history, menstrual history, and recent sexual activity to decrease the risk for inclusion of a woman with an early undetected pregnancy.

Informed Consent

10. The participant (or legally acceptable representative if applicable) has provided documented informed consent/assent for the study.

Additional Categories

11. Have an Eastern Cooperative Oncology Group (ECOG) performance status of 0 to 1 assessed within 3 days before allocation/randomization.

12. Have adequate organ function as defined in the following table ([Table 1](#)). Samples must be collected within 7 days before the start of study intervention.

Table 1 Adequate Organ Function Laboratory Values

System	Laboratory Value
Hematological	
Absolute neutrophil count (ANC)	$\geq 1500/\mu\text{L}$
Platelets	$\geq 100\,000/\mu\text{L}$
Hemoglobin	$\geq 9.0\text{ g/dL}$ or $\geq 5.6\text{ mmol/L}$ ¹
Renal	
Creatinine OR Measured or calculated ² creatinine clearance (GFR can also be used in place of creatinine or CrCl)	$\leq 1.5 \times \text{ULN}$ OR $\geq 30\text{ mL/min}$ for participant with creatinine levels $>1.5 \times$ institutional ULN
Hepatic	
Total bilirubin	$\leq 1.5 \times \text{ULN}$ OR direct bilirubin $\leq \text{ULN}$ for participants with total bilirubin levels $>1.5 \times \text{ULN}$
AST (SGOT) and ALT (SGPT)	$\leq 2.5 \times \text{ULN}$ ($\leq 5 \times \text{ULN}$ for participants with liver metastases and biliary tract cancer)
Albumin	$\geq 3\text{ g/dL}$
Coagulation	
International normalized ratio (INR) OR prothrombin time (PT) Activated partial thromboplastin time (aPTT)	$\leq 1.5 \times \text{ULN}$ unless participant is receiving anticoagulant therapy as long as PT or PTT is within therapeutic range of intended use of anticoagulants
ALT (SGPT)=alanine aminotransferase (serum glutamic pyruvic transaminase); AST (SGOT)=aspartate aminotransferase (serum glutamic oxaloacetic transaminase); GFR=glomerular filtration rate; ULN=upper limit of normal.	
¹ Criteria must be met without erythropoietin dependency and without packed red blood cell (pRBC) transfusion within last 2 weeks.	
² Creatinine clearance (CrCl) should be calculated per institutional standard.	
Note: This table includes eligibility-defining laboratory value requirements for treatment; laboratory value requirements should be adapted according to local regulations and guidelines for the administration of specific chemotherapies.	

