6.5.4 Rescue Medications and Supportive Care

Participants should receive appropriate supportive care measures as deemed necessary by the treating investigator. For participants receiving pembrolizumab + lenvatinib, suggested supportive care measures for the management of AEs with potential immunologic etiology are outlined in [Table 3](#) in Section 6.6.1.1, along with the dose modification guidelines in [Table 5](#) in Section 6.6.2. For participants receiving lenvatinib monotherapy, suggested supportive care measures and dose modification guidelines are outlined in Section 6.6.2.

Where appropriate, these guidelines include the use of oral or IV treatment with corticosteroids, as well as additional anti-inflammatory agents if symptoms do not improve with administration of corticosteroids. Note that several courses of steroid tapering may be necessary as symptoms may worsen when the steroid dose is decreased. For each disorder,

attempts should be made to rule out other causes such as metastatic disease or bacterial or viral infection, which might require additional supportive care. The treatment guidelines are intended to be applied when the investigator determines the events to be related to pembrolizumab or lenvatinib.

Note: If after the evaluation of the event, it is determined not to be related to pembrolizumab, the investigator does not need to follow the treatment guidance. Refer to [Table 3](#), [Table 4](#), and [Table 5](#) for guidelines regarding dose modification and supportive care.

It may be necessary to perform conditional procedures such as bronchoscopy, endoscopy, or skin photography as part of evaluation of the event.

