- Any progression or recurrence of any malignancy, or occurrence of another malignancy that requires active treatment. Exceptions to secondary malignancy include basal cell carcinoma of the skin, squamous cell carcinoma of the skin, new nonulcerated primary melanoma <1 mm in depth with no nodal involvement, or carcinoma in situ (eg, breast carcinoma, cervical cancer in situ) that have undergone potentially curative therapy. Exceptions should be discussed with the Sponsor before continuing therapy or remaining in follow-up.
- Confirmed radiographic disease progression outlined in Section 8.2.1.5 or Section 8.2.1.6.

Note: Participants will be permitted to continue treatment beyond iRECIST- or RANO-defined progression (Arm 1 only) after confirming informed consent addendum has been documented and after Sponsor consultation.

- Unacceptable AE(s).

A participant may be discontinued from study intervention but continue to be monitored in the study for the following reason:

- PD as determined by the investigator.

Note: Participants will be permitted to continue treatment beyond RECIST 1.1- or RANO-defined progression (Arm 1 only) as long as investigator-assessed clinical stability is observed, the participant is tolerating study intervention (Section 8.2.1.5 or Section 8.2.1.6) and after obtaining documented informed consent addendum. Treatment beyond confirmed PD per iRECIST or RANO may be permitted on Sponsor consultation.

Participants receiving the combination therapy (pembrolizumab + lenvatinib) must discontinue study therapy if any of the following occur:

ALT or AST elevation meeting the following criteria:

- ALT or AST $>5 \times$ ULN for more than 2 weeks

Pembrolizumab will have already been permanently discontinued per [Table 3](#) but lenvatinib may be administered at a reduced dose by the time this criterion is met and must be permanently discontinued immediately.

- ALT or AST $>3 \times$ ULN and (TBL $>2 \times$ ULN or INR >1.5)

Although [Table 3](#) advises pembrolizumab to be withheld (interrupted), and [Table 5](#) advises lenvatinib to have no dose modification or a reduction, if this criterion is met, both interventions must be permanently discontinued immediately.

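### Table 1 admits some participants with liver metastases or biliary tract cancer on liver values that, unchanged, meet the mandatory permanent stop of both drugs in Sections 6.6.3 and 7.1

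*Combined protocol and SAP*

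**What the plan says.** **Entry (Section 5.1, Table 1).** ALT and AST may be up to 2.5 x ULN, raised to 5 x ULN "for participants with liver metastases and biliary tract cancer". I read this as either condition. Total bilirubin must be at most 1.5 x ULN. Alternatively, direct bilirubin must be within normal limits "for participants with total bilirubin levels" above 1.5 x ULN, and that branch puts no ceiling on the total. INR, PT and aPTT must be at most 1.5 x ULN, "unless participant is receiving anticoagulant therapy as long as PT or PTT is within therapeutic range of intended use of anticoagulants". Section 6.5.1 allows warfarin, heparin and anti-Xa agents on study.

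**Stop (Section 6.6.3, item 3).** "Participants receiving the combination therapy (pembrolizumab + lenvatinib) must discontinue study therapy if any of the following occur". Two criteria follow. The first is "ALT or AST >5 X ULN for more than 2 weeks". The second is ALT or AST above 3 x ULN together with total bilirubin above 2 x ULN or INR above 1.5. For the second, the text acknowledges that Tables 3 and 5 advise milder action and overrides them: "if this criterion is met, both drugs must be permanently discontinued immediately". Section 7.1 restates it: "if this criterion is met, both interventions must be permanently discontinued immediately". Neither section mentions screening values, direct bilirubin or anticoagulants, and the country-specific requirements in Appendix 7 add no exception.

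**The concern.** The second criterion uses thresholds that Table 1 allows some participants to exceed on the day they enter. A site that follows both texts to the letter would enrol and dose such a person, then withdraw both drugs permanently although nothing had changed. A site that treats the values as that person's baseline would be departing from a hepatic safety stop worded as mandatory and immediate. Neither position is good for a site, and the protocol does not say which to take.

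**Working it through.** The plan gives no figure to reproduce here, so the check compares the limits directly.

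| Quantity | Entry limit (Table 1) | Stop (6.6.3, 7.1) | Overlap |
|---|---|---|---|
| ALT/AST, liver metastases or BTC | <=5 x ULN | >3 x ULN | >3 to 5 x ULN (5 - 3 = 2 x ULN wide) |
| ALT/AST, all others | <=2.5 x ULN | >3 x ULN | none (2.5 < 3) |
| ALT/AST, liver metastases or BTC, against the other hepatic stop | <=5 x ULN | >5 x ULN for over 2 weeks | none |
| Total bilirubin, direct <=ULN | no cap | >2 x ULN | any value >2 x ULN |
| INR, therapeutic anticoagulation | limit waived | >1.5 | any therapeutic value >1.5 |
| INR, no anticoagulant | <=1.5 x ULN | >1.5 (absolute) | depends on local ULN |

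The last row needs an assumption, because the documents give no INR ULN. At ULN 1.0 the entry limit is 1.5 x 1.0 = 1.50, so there is no overlap. At 1.1 it is 1.65, an overlap of >1.5 to 1.65. At 1.2 it is 1.80, an overlap of >1.5 to 1.80.

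**Bilirubin example.** ALT 4 x ULN, total bilirubin 2.2 x ULN, direct bilirubin <=ULN, liver metastases present.
- Entry: 4 <= 5, and 2.2 > 1.5 with direct <=ULN, so eligible.
- Stop: 4 > 3 and 2.2 > 2, so met.

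**INR example.** ALT 3.25 x ULN, INR 1.55, normal bilirubin, liver metastases present.
- Entry: 3.25 <= 5. The INR passes under the waiver if the participant is therapeutically anticoagulated, or without it if the local ULN is 1.1 (1.55 <= 1.65).
- Stop: 3.25 > 3 and 1.55 > 1.5, so met.

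Applying both rules over a grid (ALT/AST 0.5 to 5.75 x ULN, total bilirubin 0.5 to 4 x ULN, direct bilirubin 0.8 or 1.2 x ULN, INR 0.9 to 3.05) gives the same pattern. Joint hits occur only with liver metastases or BTC.

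**Exposure before the stop is met, bilirubin route.** As the chemistry row of the Schedule of Activities reads, the first on-treatment sample is Cycle 1 Day 15. I assume no missed doses and a sample taken before that day's dose.
- Pembrolizumab: 1 of up to 35 administrations.
- Lenvatinib: Days 1 to 14, so 14 doses.
- Visit window of 3 days either way (Day 12 to Day 18): 11 to 17 doses.
- Laboratory window of 72 hours before the visit: 12 - 3 = Day 9, so 8 doses at the earliest. The range is roughly 8 to 17.

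**INR route.** The timing is open. After screening, coagulation tests are taken only as clinically indicated in anticoagulated participants.

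**The case against.** The strongest reply is that the stop concerns treatment-emergent toxicity.
- Section 6.6.3 is about attributing treatment-related events, and its criteria must occur.
- Section 6.5.4 says: "The treatment guidelines are intended to be applied when the investigator determines the events to be related to pembrolizumab or lenvatinib".
- The stop is phrased as an override of Tables 3 and 5, which concern immune-related and lenvatinib-related events. The same phrasing recurs in Section 7.1.
- Appendix 3 does not count a pre-existing condition that has not worsened as an adverse event.
- If toxicity rules ignored baseline, the Table 3 instruction to withhold pembrolizumab would also catch people on their entry values, which would defeat the 5 x ULN allowance.

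This stands as a plausible reading, and perhaps the intended one. It does not settle the text. The sentence in Section 6.5.4 belongs to guidance that refers to Tables 3 to 5, and this stop is set above Tables 3 and 5. Section 7.1 states the criterion with no baseline or relatedness condition of its own. Elsewhere the protocol writes baseline into a rule when it wants it there: QTc recovery in Section 6.6.2.10, weight in note d of Table 5, and liver enzymes in Table 3.

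Two entry rules narrow the group without closing the gap. Exclusion 32 may keep some candidates out, but it rests on the investigator's opinion. Child-Pugh class A, which counts bilirubin and INR or PT, applies only to Cohort F, and the documents do not give its component cut-offs. Cohort E is largely outside the issue because extracranial disease is excluded.

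It is also fair to say that a site applying the stop literally errs on the cautious side.

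**Conclusion.** The overlap is real as written and minor. It affects only combination-arm participants with liver metastases or BTC who enter with ALT/AST above 3 and up to 5 x ULN. They must also have total bilirubin above 2 x ULN with normal direct bilirubin, or INR above 1.5 (on therapeutic anticoagulation, or without it where the local INR ULN exceeds 1.0). The number of such participants cannot be estimated from the documents.

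A reader might infer three stronger things, none of which the documents support:
- That these participants will certainly lose treatment. The treatment-emergent reading is open to a site.
- That the response rate is biased. Section 5.5 does not replace participants who discontinue, but without a count or any response data no effect on ORR can be claimed.
- That the hepatic stops are generally too strict or conflict with entry throughout. The criterion above 5 x ULN begins where the entry limit ends, and participants without liver metastases or BTC are unaffected.

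**What to change.** For every cohort still enrolling, add one line to Table 1 that applies to all participants: *Participants with ALT or AST >3 x ULN and (total bilirubin >2 x ULN or INR >1.5) at screening are not eligible.* Leave the stop in Sections 6.6.3 and 7.1 unchanged. The line closes the bilirubin route and both INR routes. It uses tests already in the screening schedule. Its cost is a few excluded candidates. In Cohort D it should apply before randomization, so that both arms keep the same entry rule.

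Section 9.9 says that Cohorts A and B have stopped enrolling. The documents do not state the status of the others, so the line may reach few cohorts. Anyone already on treatment whose screening values met the criterion should be referred to the sponsor's hepatic safety review.

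I would not write substitute stop triggers for such participants. A rule tied to the Table 1 limits, for example, could let ALT rise to 5 x ULN and total bilirubin rise without limit while direct bilirubin stayed normal.
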